#### **11.2.2.1.1 Efficacy**

The primary efficacy endpoint is the change from Baseline in serum LDL-C at Week 16. Baseline is defined as the last non-missing LDL-C value prior to the first dose of study drug.

Exploratory comparisons between elobixibat 5 mg and placebo will be performed for the following secondary efficacy endpoints:

- Absolute change from Baseline to Week 16 in liver fat fraction (%) as measured by MRI-PDFF
- Absolute change from Baseline to Week 16 in total liver fat (mL) as measured by MRI

The analysis methods for the other secondary and exploratory endpoints will be detailed in the statistical analysis plan (SAP).

#### **11.2.2.1.2 Safety**

The safety endpoints for this study include clinical laboratory assessments, vital signs, AEs, ECGs, physical examinations, and concomitant medications.

AEs will be coded using the latest version of the Medical Dictionary for Regulatory Activities (MedRA). TEAEs will be defined as AEs that are new or worsening after the first dose of study drug. A general summary of patients with TEAEs and serious adverse events (SAEs) will be tabulated with numbers and percentages of patients and repeated for severity and relationship to study drug per treatment group. The number of AEs leading to withdrawal and SAEs leading to death will also be summarized. The incidence of TEAEs will be summarized by body system and treatment group.

The safety laboratory data will be summarized by visit and by treatment group, along with changes from Baseline. Values outside of the reference range will be flagged and laboratory abnormalities of special interest will be summarized.

#### **11.2.2.2 Missing Data**

Missing data handling for the primary efficacy endpoint will be specified in the SAP.

#### **11.2.2.3 Demographic and Baseline Characteristics**

Descriptive summaries of demographics and other baseline characteristics (including medical and surgical history) will be presented by treatment group and overall using the ITT population.

Prior medication will be summarized by treatment group and overall using the ITT population.

#### **11.2.2.4 Subject Disposition**

The following will be summarized descriptively (by treatment group and overall where applicable):

- Patients enrolled (who signed the informed consent)
- Patients randomized
- Patients treated
- Patients completing the study
- Patients withdrawing early (including withdrawal reason)

#### **11.2.2.5 Evaluation of Primary Efficacy Endpoints**

An analysis of covariance (ANCOVA) will be used to analyze the primary efficacy endpoint. The model will include treatment arm and Baseline LDL-C scores.

Least square (LS) mean (SE), LS mean difference (SE), 95% confidence intervals, and *P*-values between elobixibat 5 mg and placebo will be provided. The model assumptions will be checked before the analysis. If there are concerns on model assumptions, i.e.,

normality and homogeneity of variances, a non-parametric ANCOVA based on the rank scores can be used as a sensitivity analysis.

Sensitivity analyses may be performed and will be detailed in the SAP.

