### **11.1 Sample Size and Power**

Due to the exploratory nature of this study, no formal power calculations were used to determine the sample size. The number of subjects (46 patients in total, 23 patients per treatment group) was chosen based on clinical experience with other similar proof-of-concept studies.

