## **2 STATISTICAL CONSIDERATIONS**

### **2.1 GENERAL CONSIDERATIONS**

General principles will be followed:

- Population summaries (e.g., disposition, demographics and baseline characteristics, medical/surgical history, prior and concomitant medications) and efficacy tables will summarize data by the randomized treatment group. Safety tables will be summarized by the actual treatment subject received.
- All continuous variables will be summarized using descriptive statistics including the number of patients with data to be summarized (n), mean, standard deviation (SD), median, minimum (min) and maximum (max). Minimum and maximum will be displayed with a maximum of 2 decimal places. Mean and median will be rounded to 1 additional decimal place, SD will be rounded to 2 additional decimal places, compared to the displayed minimum and maximum.
- Categorical variables will be summarized with count and percent; the denominator will be based on the number of subjects in the treatment group, unless otherwise stated.
- In general, efficacy analysis will be performed using the intent-to-treat (ITT) population and safety analyses will be performed using the safety population. Per-protocol population will be used for the primary endpoint sensitivity analysis.

- The default significance level will be (5%); confidence intervals (CIs) will be 95% and all tests will be two-sided, unless otherwise specified in the description of the analyses.
- P-values will be rounded to three decimal places. If a p-value is less than 0.001, it will be reported as “<0.001.” If a p-value is greater than 0.999 it will be reported as “>0.999”.

All analyses will be performed using SAS®, Version 9.4 or higher.

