### **Sensitivity Analysis for primary endpoint**

Mixed models repeated measures (MMRM) analysis based on both imputed data and observed data will be used as sensitivity analysis. The explanatory variables will include treatment, week, baseline value, baseline lipid lowering medications, treatment-by-week interaction, and treatment-by-baseline interaction, with unstructured covariance model across week. The average treatment effect at Week 16 (lsmeans with 95% CI for each treatment group and lsmean difference with 95% CI) will be provided as both tables and figures. Additional MMRM analyses may include the addition of other model covariates such as age at baseline, sex, and baseline FIB-4 (dichotomized at  $\geq 1.3$ ). An additional series of models may include percent change from baseline as the dependent variable.

A plot of fitted values versus residuals and the residual QQ Plot will be used to check the ANCOVA model assumptions. If there are concerns about the model assumptions, i.e., normality and homogeneity of variances, a non-parametric ANCOVA based on the rank scores will be used as a sensitivity analysis as well.

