### **Secondary Efficacy Endpoints**

A summary of descriptive statistics of the absolute change from baseline to week 16 in liver fat fraction (%) as measured by MRI-PDFF and total liver fat (mL) as measured by MRI will be provided.

The test results and changes from baseline at each scheduled time point, including week 16 and Follow-up, will be summarized for the following variables:

- Serum ALT, AST, and gamma-glutamyl transferase
- HDL-C, non-HDL-C, LDL-C/HDL-C ratio, and triglycerides
- Total bile acids

The minimum and maximum post baseline value for each above lab test will be included in the visit summaries.

The change from baseline at week 16 will be analyzed using the analysis of covariance (ANCOVA) with the treatment group as a factor and the corresponding baseline value as a covariate. The model assumptions for each secondary efficacy endpoint will be evaluated before the analysis. If there are concerns about the model assumptions, i.e., normality and homogeneity of variances, non-

parametric ANCOVA based on the rank scores will be used. No missing data imputation for secondary efficacy endpoints.

MMRM figures of change from baseline by study arm and the difference between study arms will be generated for all secondary endpoints.

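### For secondary endpoints the SAP answers unequal variances with a rank ANCOVA, which does not cure them and gives no result in the endpoint's units (minor; for LDL-C it is only a sensitivity analysis)

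*Protocol*

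**What the plan says.** Three places use the same trigger and the same remedy.

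- **Protocol 11.2.2.5 (LDL-C).** "Least square (LS) mean (SE), LS mean difference (SE), 95% confidence intervals" and P-values are promised without condition. On assumptions, the text continues: "normality and homogeneity of variances, a non-parametric ANCOVA based on the rank scores can be used as a sensitivity analysis".
- **SAP 3.2, Sensitivity Analysis for primary endpoint (LDL-C).** The optional wording becomes firm but keeps its supplementary role: "normality and homogeneity of variances, a non-parametric ANCOVA based on the rank scores will be used as a sensitivity analysis as well".
- **SAP 3.2, Secondary Efficacy Endpoints.** The Week 16 change is analysed by ANCOVA with treatment group and baseline value. If the same two assumptions are in doubt, the sentence ends (the quotation starts after the prefix non-): "parametric ANCOVA based on the rank scores will be used. No missing data imputation for secondary efficacy endpoints". It is not called a sensitivity analysis here, and nothing says that the mean-based ANCOVA is still reported.

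The secondary endpoints covered are liver fat fraction, total liver fat, ALT, AST, gamma-glutamyl transferase, several lipids and total bile acids.

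No method that allows the variance to differ by arm appears in either document. The SAP Appendix ANCOVA code has one residual variance, and the MMRM code fits one covariance matrix for both arms.

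**The concern.** Non-normality and unequal variances are different failures, and one remedy is named for both. Ranking may help with the first. It does not help with the second. The null hypothesis of a rank ANCOVA is that the arms have the same distribution given baseline. A difference in spread breaks that null even when the mean changes are equal, and ranking does not equalise the spread.

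Unequal spread is plausible here. If only some treated patients respond, the active arm becomes more variable. Unequal arm sizes are plausible too. Secondary endpoints are analysed without imputation, Protocol 5.4 names diarrhea as the leading dose-limiting side effect, and SAP section 4 records missed visits.

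At stake is a secondary comparison, liver fat included, whose test statistic answers a different question from the planned mean difference and carries no estimate in percentage points, mL or U/L.

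**Working it through.** **Inputs from the documents.** 23 patients per arm (Protocol 11.1); two-sided 5% level (SAP 2.1); secondary model of treatment plus baseline on observed cases (SAP 3.2). There is no planned figure to reproduce: "no formal power calculations were used to determine the sample size", and no SD, skewness or dropout rate is given.

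**Assumptions.** Change = -0.3 × centred baseline + error. Error SD is 20 in placebo and 20 × ratio in active, with ratio 1.5 to 2. The true mean difference is zero. Errors are normal or centred log-normal with σ = 0.4 or 0.6. Log-normal skewness is (w + 2)√(w − 1) with w = exp(σ²), which gives 1.3 and 2.3. There were 10,000 trials per cell, so the simulation SE at 5% is √(0.05 × 0.95 / 10,000) = 0.2 points.

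**Step 1. Rejection of equal means at nominal 5%, SD ratio 1.5 to 2.**

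| Setting | Rank ANCOVA | Ordinary ANCOVA | ANCOVA with HC3 |
|---|---|---|---|
| 23 v 23, normal | 5.7–6.2% | 5.1–5.9% (all three error types) | 4.3–5.3% (all three) |
| 23 v 23, skewness 1.3 | 6.6–9.3% | | |
| 23 v 23, skewness 2.3 | 8.2–14.0% | | |
| 16 active v 23 placebo, all error types | 6.5–14.8% | 6.7–8.8% | 4.5–6.1% |

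Two further independent runs agree. At 23 v 23 they gave rank 5.4–5.9% with normal errors, with a highest skewed-error value of 13.4% in one run and 13.9% in the other; ordinary 4.9–6.0%; HC3 4.2–5.1%. ANCOVA with arm-specific variance and approximate degrees of freedom gave 4.6–5.6% at 23 v 23, and 5.0–6.5% at 16 v 23. Quade's form of rank ANCOVA gives nearly the same values as ranking change and baseline (13.9% v 14.0%).

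**Step 2. Other error shapes** (baseline SD 25, slope −0.4, SD ratio 2, 23 v 23).

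| Errors | Rank | Ordinary | HC3 |
|---|---|---|---|
| Normal | 5.8% | 5.0% | 4.4% |
| t, 5 df | 6.0% | 5.1% | 4.3% |
| Gamma, skewness 1 | 8.7% | 5.6% | 5.0% |
| Exponential | 16.9% | 6.1% | 5.6% |
| Log-normal, σ = 0.8 | 18.4% | 6.5% | 5.7% |

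With equal variances the rank test rejects 4.7–5.1%. The excess therefore comes from unequal spread combined with skew. With symmetric errors and equal arms it is about 1 point.

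**Step 3. Why ordinary ANCOVA holds in equal arms but not in unequal ones.** True variance of the difference is σ_A²/n_A + σ_P²/n_P. The pooled analysis uses s_p²(1/n_A + 1/n_P), where s_p² is the df-weighted mean of the two variances. With n_A = n_P the two agree in expectation. With n_A = 16, n_P = 23, σ_A = 40, σ_P = 20 (baseline term ignored):

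- True: 1600/16 + 400/23 = 117.4.
- s_p² = (15 × 1600 + 22 × 400)/37 = 886.5; pooled: 886.5 × (1/16 + 1/23) = 93.9.
- SE ratio: √(93.9/117.4) = 0.895. The effective cut-off is 1.96 × 0.895 = 1.75, so the two-sided rate is about 8.0%.

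With σ_A = 30 the same steps give 63.9 against 73.6, SE ratio 0.931, and about 6.8%. Both fit the simulated 6.7–8.8%. At SD ratio 2 with 17 or 15 active patients, ordinary ANCOVA gave 7.4–10.0% across all error shapes. Unequal variance does need a remedy once arm sizes differ, but ranks are not it.

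**The case against.** The best counter-case has four parts.

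1. **LDL-C loses nothing.** A reader might infer that the primary analysis switches to ranks and the mg/dL effect disappears. The documents do not support this. The LS mean difference and CI are unconditional in Protocol 11.2.2.5 and in the SAP imputation steps 5 and 6. The MMRM also gives a Week 16 difference in LDL-C units, and the rank analysis is explicitly supplementary. This stands.
2. **Secondary endpoints keep other estimates.** A reader might infer that a switched endpoint has no effect size at all. SAP 3.2 still requires descriptive statistics and MMRM figures of the between-arm difference for all secondary endpoints. This stands in part. What is missing is an estimate from the test that is used, and the sample MMRM code also pools the variance across arms.
3. **14% is not a false-positive rate caused by unequal variances.** That cell needs skewness 2.3 and an SD ratio of 2. There the median is about −0.25 SD, so the arm medians are −0.25 × 20 = −5 and −0.25 × 40 = −10 mg/dL. The arms do differ in distribution, and the rank test detects that. This stands. The figure measures how far the rank test departs from a test of means under stated assumptions. It is neither a maximum (Step 2 reaches 18.4%) nor a rate for an inert drug.
4. **The simulation is simplified.** It omits the treatment-by-baseline term, the lipid-medication covariate and the imputation used for LDL-C. That limits its use for LDL-C. The secondary model as written has only treatment and baseline, without imputation, which is what was simulated.

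Protocol 11.2.2.1.1 also calls the two liver-fat comparisons exploratory, which lowers the stakes.

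**Conclusion.** The secondary-endpoint rule in SAP 3.2 is wrong as written, with minor severity. It names unequal variances as a trigger and then prescribes a method that neither addresses them nor estimates the planned mean difference. Under equal means with an assumed SD ratio of 1.5 to 2, the departure from 5% at 23 v 23 is slight with normal errors (about 5 to 6%) and material with skewed ones (about 7 to 14% for skewness 1.3 to 2.3). Ordinary ANCOVA stays at about 5 to 6% and the variance-robust versions at 4 to 6%. With 16 active v 23 placebo and the active arm more variable, ordinary ANCOVA rises to about 6 to 10%, and the robust versions stay near 5 to 7%. That scenario assumes about 30% loss (7 of 23) in one arm only, which the documents neither state nor exclude.

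For LDL-C the impact is low. The only gap is that no planned sensitivity analysis addresses unequal variances between arms.

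**What to change.** **SAP 3.2, Secondary Efficacy Endpoints.** Separate the two triggers. If homogeneity of variances is the concern, keep the ANCOVA on the original scale and let the residual variance differ by arm (PROC MIXED with `REPEATED / GROUP=trtp` and `DDFM=KR`), or use HC3 standard errors. Choose one in advance. Report the LS mean difference and 95% CI from that model. If normality is the concern, a rank ANCOVA may be shown beside the mean-based estimate, not in place of it.

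**Protocol 11.2.2.5 and SAP 3.2, Sensitivity Analysis for primary endpoint.** Add the same variance-robust ANCOVA as the LDL-C sensitivity analysis for unequal variances. Its estimate and standard error go straight into the PROC MIANALYZE step already planned. The SAP gives no rule for combining a rank ANCOVA over the 200 imputed data sets.

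**Cost.** A few sentences of SAP text and one line of code. HC3 is slightly conservative when variances are equal (about 4 to 4.6% against 5%) and loses a little power. In simulated responder-subset cases it gave 34% against 37% for ordinary ANCOVA (30% of patients responding by −40 mg/dL) and 27% against 30% (20% responding by −60 mg/dL). The rank ANCOVA gave 31% and 21% in the same cases. Heavy-tailed errors, where ranks may gain power, were not examined for power. The arm-specific variance model was simulated with approximate degrees of freedom, not with the Kenward-Roger option itself.

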#### **11.2.2.6 Evaluation of Secondary and Exploratory Efficacy Endpoints**

Descriptive statistics will be provided for secondary and exploratory endpoints listed in Sections 9.1.2 and 9.1.3, respectively, unless otherwise specified.

#### **11.2.2.7 Evaluation of Safety Endpoints**

Safety data will be analyzed using descriptive statistics and summaries by treatment group of SAEs, AEs, vital signs, clinical safety laboratory tests (hematology, coagulation, clinical chemistry, and urinalysis), and concomitant medication. Analyses will be performed using the safety analysis set.

Summaries of AEs (coded according to the MedDRA system organ class [SOC] and MedDRA preferred term) will include the following:

- Overview of the incidence of TEAEs (TEAEs, drug-related TEAEs, TEAEs leading to study discontinuation, and treatment-emergent SAEs)
- TEAEs by SOC and preferred term
- Intensity of TEAEs by SOC and preferred term
- Drug-related TEAEs by SOC and preferred term
- TEAEs leading to study discontinuation by SOC and preferred term
- Treatment-emergent SAEs by SOC and preferred term

Concomitant medication use during the treatment period will be summarized by Anatomical Therapeutic Chemical (ATC) class and World Health Organization (WHO) preferred name.

Summaries of vital signs will be presented. For each visit, the actual results, the change from Baseline, and the observed post-baseline value will be presented.

Summaries of clinical safety laboratory data will be presented. For each visit, the actual result, the change from Baseline, and the observed post-baseline value will be presented.

---

Data listings will be provided for each patient for all safety parameters.

#### **11.2.2.8        Compliance and Exposure**

Exposure will be analyzed by calculating the number of days with exposure to study drug. Results will be presented by treatment group using the safety analysis set.

The percentage compliance will be described by treatment group and the number of patients with a compliance <80%, between 80% and 120%, and >120% will be presented based on the safety analysis set.

**12. DIRECT ACCESS TO SOURCE DATA/NOTES**

The Investigator/institution shall provide direct access to source data/documents for study-related monitoring, audits, IRB review, and regulatory inspection.

## **13. QUALITY CONTROL AND QUALITY ASSURANCE**

### **13.1 Conduct of the Study**

The study team shall implement and maintain quality control and quality assurance procedures with written SOPs to ensure that the study is conducted, and data are generated, documented, and reported in compliance with the protocol, ICH GCP, and applicable regulatory requirements.

This study shall be conducted in accordance with the provisions of the Declaration of Helsinki (October 1996) and all revisions thereof, and in accordance with US Food and Drug Administration (FDA) regulations (Code of Federal Regulations, Sections 312.50 and 312.56) and with ICH GCP (CPMP 135/95).

The Investigator may not deviate from the protocol without a formal protocol amendment having been established and approved by an appropriate competent authority and IRB, except when necessary to eliminate immediate hazards to the patient or when the change(s) involve(s) only logistical or administrative aspects of the study. Any deviations may result in the patient having to be withdrawn from the study and render that patient non-evaluable.

### **13.2 Study Monitoring**

Before study initiation, at a site initiation visit or at an Investigator's meeting, a Sponsor representative or designee will review the protocol and eCRF with the Investigators and the investigative staff. During the study, the clinical monitor (the CRA) will visit the site regularly to check the completeness of patient records, the accuracy of entries on the eCRFs, the adherence to the protocol and to GCP, the progress of enrollment, and to ensure that study drug is being stored, dispensed, and accounted for according to specifications.

The investigator must ensure that eCRFs are completed within a timely period of patient visits, as per individual site agreements, and must allow the CRA and the Sponsor representative or designee periodic access to patient records and all study-related materials, including relevant hospital or clinical records, to confirm their consistency with the eCRF entries. No information in these records about the identity of the patients will leave the study center. The Sponsor monitoring standards require full verification for the presence of the signed ICF, adherence to the inclusion/exclusion criteria,

---

documentation of SAEs, and recording of primary efficacy and safety variables. The CRA will review source data compared with the eCRFs and will verify source data according to the study-specific monitoring plan. The design of the study, the frequency of patient visits, and the site enrollment rate will determine the frequency of monitoring visits. Upon study completion, the CRA will visit the site to conduct a study termination visit, which will include collection of any outstanding documentation.

It is recommended that the Investigator/investigative staff log into the eCRF system every working day or at minimum twice weekly in order to provide a prompt response to queries. The Investigator/investigative staff should respond to queries and make any relevant changes to the study data within 3 working days.

## **14. ETHICS**

### **14.1 Institutional Review Board**

Prior to the start of the study, the Investigator is responsible for ensuring that the protocol and consent form have been reviewed and approved by a relevant IRB. The IRB shall be appropriately constituted and perform its functions in accordance with FDA, ICH, GCP, and local requirements as applicable.

The IRB shall approve all protocol amendments (except for logistical or administrative changes), written informed consent documents and document updates, patient recruitment procedures (e.g., advertisements), written information to be provided to the patients and caregivers, the Investigator's Brochure, available safety information, information about payment and compensation available to patients, the Investigator's curriculum vitae and/or other evidence of qualifications and any other documents requested by the IRB and regulatory authority (competent authority) as applicable.

### **14.2 Written Informed Consents**

The Investigator (physician) or investigative staff, in accordance with local regulations, will explain to each patient (or legally authorized representative) the nature of the study, its purpose, the procedures involved, the expected duration, alternative treatment, the potential risks and benefits involved, and any discomfort that may occur. Each patient will be informed that participation in the study is voluntary and that he/she may withdraw from the study at any time and that withdrawal of consent will not affect his/her subsequent medical treatment or relationship with the treating physician.

If written consent is not possible, oral consent can be obtained if witnessed and followed by a signed statement from one or more persons not involved in the study, indicating why the patient was unable to sign the form. No patient can enter the study before his/her informed consent has been obtained, as required by country regulations.

The ICF is part of the protocol and must be submitted by the Investigator/investigative staff with the protocol for IRB approval. The Sponsor will supply an ICF which complies with regulatory requirements and country laws and is considered appropriate for the study. Any changes to the ICF suggested by the Investigator must be agreed to by the Sponsor before submission to the IRB and a copy of the approved version must be provided to the clinical monitor after IRB approval.

